To assess effects on cognition over a 12-week treatment period	 Change from baseline to Week 12 in Cogstate neurocognitive battery with a focus on attention/reaction time, verbal learning and working memory) Change from baseline to Week 12 in PedsQLTM Cognitive Functioning Scale
To explore the effects of a 12-week treatment with RO7017773 compared with placebo in core and associated symptoms of ASD as measured by digital biomarkers and to evaluate the feasibility of implementation of digital biomarkers in a clinical study setting	 Change from baseline to Week 12 in core and associated symptoms of ASD (including sociability, communication deficits, restricted and repetitive behaviors, spatial working memory, anxiety and sleep) as measured remotely with digital health technology Adherence to the digital biomarker schedule of assessments between baseline and Week 12

Feedback from support persons or parents will be collected with entry and exit questions at baseline and at the end of the study, respectively.

4. STUDY DESIGN

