8.2.7 Cognitive Assessments and Measures of Somnolence or Sudden Onset of Sleep

As part of the safety assessments, support persons will complete the PedsQL™ Cognitive Functioning Scale and participants will be asked to perform a number of cognitive assessments designed to measure specific areas of cognition. The description of these assessments is included in Section 8.1.5.9 (PedsQL™ Cognitive Functioning Scale) and Section 8.1.5.10(Neurocognitive Battery). The KSS, ESS or ESS-CHAD scales, and the Sudden Onset of Sleep Questionnaire will be used to assess somnolence and sudden onset of sleep. These scales and questionnaires are described in Section 8.1.5.11, Section 8.1.5.12, Section 8.1.5.13, and Section 8.1.5.14.

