9.3 POPULATIONS FOR ANALYSES

For purposes of analysis, the following populations are defined in Table 11.

Table 11 Analysis Populations

Population	Description
Safety	All participants randomized to study treatment and who received at least one dose of the study treatment, whether prematurely withdrawn from the study or not, will be included in the safety analysis.
Pharmacokinetic	All participants providing pharmacokinetic data will be included in the PK Population. Participants will be excluded from the PK analysis population if they significantly violate the inclusion or exclusion criteria, deviate significantly from the protocol, or if data are unavailable or incomplete which may influence the PK analysis. Excluded cases will be documented together with the reason for exclusion. All decisions on exclusions from the analysis will be made prior to database closure.
Efficacy	All participants who give informed consent, are randomized, and receive at least one dose of double-blind study medication. Data will be analyzed as per the actual treatment received.

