9.4.3 Safety Analyses

All safety analyses will be based on the safety analysis population.

Table 13 Safety Statistical Analysis Methods

Endpoint	Statistical Analysis Methods
Adverse events	The original terms recorded on the eCRF by the Investigator for AEs will be coded by the Sponsor.
	Adverse events will be summarized by mapped term and appropriate thesaurus level.
Clinical laboratory tests	All clinical laboratory data will be stored on the database in the units in which they were reported. Laboratory test values will be presented in International System of Units (SI units; Système International d'Unités) by tabular summaries and individual listings with flagging of abnormal results.
Vital signs	Vital signs data will be presented by individual listings with flagging of values outside the normal ranges and flagging of abnormalities. In addition, tabular summaries of raw values and change from baseline will be used, as appropriate.
ECG	ECG data will be presented by individual listings. In addition, tabular summaries of raw values and change from baseline will be used, as appropriate.
Concomitant medications	The original terms recorded on the participants' eCRF by the Investigator for concomitant medications will be standardized by the Sponsor by utilizing a mapped term and appropriate drug dictionary level.
	Concomitant medications will be presented in summary tables and listings.
C-SSRS, PedsQL™ Cognitive Functioning Scale, and cognitive	Data will be presented in summary tables and listings
assessments,	
KSS, ESS or ESS- CHAD, and	
Sudden Onset of	
Sleep Questionnaire	

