3. ANALYSIS SETS

The analysis data sets for the purposes of analyses are presented in Table 3.

Efficacy analyses based on the Efficacy Analysis Population will be restricted in a way that assessments at week 12 will be excluded from the efficacy analyses if the participant missed more than 7 consecutive study medications immediately preceding the day of the assessment (if performed), or if the overall IMP compliance, i.e. the ratio of administered study medication to planned study medication until the assessment, was < 60%.

Post treatment EEG assessments will be excluded from the PD analysis if the last dose of study medication was taken more than 6 hours before the EEG. Additionally, Week 2 and Week 12 EEG assessments will be excluded from the PD analysis if the study participant missed more than 3 doses in the week preceding the EEG.

Table 3 Analysis Sets

Population	Description
Safety Population	All participants randomized to study treatment and who received at least one dose of the study treatment, whether prematurely withdrawn from the study or not, will be included in the safety analysis.

Pharmacokinetic Population	All participants providing pharmacokinetic data will be included in the PK Population. Participants will be excluded from the PK analysis population if they significantly violate the inclusion or exclusion criteria, deviate significantly from the protocol, or if data are unavailable or incomplete which may influence the PK analysis. Excluded cases will be documented together with the reason for exclusion.
Efficacy Analysis Population	All participants who give informed consent, are randomized, and receive at least one dose of double-blind study medication.

4. STATISTICAL ANALYSES

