4.4 SAFETY ANALYSES

All safety analyses will be based on the safety analysis population.

 Table 10
 Safety Statistical Analysis Methods

Endpoint	Statistical Analysis Methods
Adverse events	The original terms recorded on the eCRF by the Investigator for AEs will be coded by the Sponsor. Adverse events will be summarized by mapped term and appropriate thesaurus level.
Clinical laboratory tests	All clinical laboratory data will be stored on the database in the units in which they were reported. Laboratory test values will be presented by tabular summaries, plots, and individual listings with flagging of abnormal results. Hereby, by default the International System of Units (SI units; Système International d'Unités) will be applied, and values will be transformed to common Roche standard reference range (following Roche Safety Lab Standardisation Guidance) where applicable.
Vital signs	Vital signs data will be presented by individual listings with flagging of values outside the normal ranges and flagging of abnormalities. In addition, tabular summaries of raw values and change from baseline will be used, as appropriate.
ECG	ECG data will be presented by individual listings. In addition, tabular summaries of raw values and change from baseline will be used, as appropriate.
Concomitant medications	The original terms recorded on the participants' eCRF by the Investigator for concomitant medications will be standardized by the Sponsor by utilizing a mapped term and appropriate drug dictionary level. Concomitant medications will be presented in summary tables and listings.
C-SSRS, Neurocognitive Battery, KSS, ESS or ESS-CHAD, and Sudden Onset of Sleep Questionnaire	Data will be presented in summary tables and listings

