t_<>	Efficacy	Correlation between Baseline EEG beta power and clinical efficacy	
t_pql_tot_cfb	Efficacy	PedsQL™ Total Score Change from Baseline	
t_pql_cfs_cfb	Efficacy	PedsQL [™] Cognitive Functioning Score Change from Baseline	
g_cgii	Efficacy	CGI-I Overall Score over Time	
g_cgis	Efficacy	CGI-S Overall Score over Time	
g_forest	Efficacy	Vineland-3 ABC GSV composite	

	•		
		by Geographic Region with 80% CI	
g_forest	Efficacy	Vineland-3 ABC GSV composite by Rater Change with 80% CI	
g_forest	Efficacy	Vineland-3 ABC GSV composite by Site Type with 80% CI	
g_forest	Efficacy	Vineland-3 ABC GSV composite by Age Category with 80% CI	
g_forest	Efficacy	Vineland-3 ABC GSV composite by IQ Category with 80% CI	
g_forest	Efficacy	RBS-R total score by Geographic Region with 80% CI	
g_forest	Efficacy	RBS-R total score by Rater Change with 80% CI	
g_forest	Efficacy	RBS-R total score by Site Type with 80% CI	
g_forest	Efficacy	RBS-R total score by Age Category with 80% CI	
g_forest	Efficacy	RBS-R total score by IQ Category with 80% CI	
g_forest	Efficacy	RBS-R total score by Diagnosis of Anxiety at Baseline with 80% CI	
g_forest	Efficacy	RBS-R total score by Sex with 80% CI	
g_forest	Efficacy	CRRI total score by Sex with 80% CI	
g_forest	Efficacy	CGII (RRB domain) by Sex with 80% CI	
g_forest	Efficacy	BAI total score by Diagnosis of Anxiety at Baseline with 80% CI	

Certificate Of Completion

Envelope Id: 00A25604873540C595AE83AF56584F0E

Subject: Complete with Docusign: BP41316_SAP_V02.pdf

Source Envelope:

Document Pages: 51 Signatures: 1 Certificate Pages: 4 Initials: 0

AutoNav: Enabled

Envelopeld Stamping: Disabled

Time Zone: (UTC+01:00) Amsterdam, Berlin, Bern, Rome, Stockholm, Vienna

Status: Completed

Envelope Originator:

[name]

IP Address:

Record Tracking

Status: Original

6/28/2024 1:54:12 PM

Holder:

Location: DocuSign

Signer Events

Statistician

F. Hoffmann-La Roche

Security Level: Email, Account Authentication

(Required)

Signature

Timestamp

Sent: 6/28/2024 1:54:56 PM Viewed: 6/28/2024 1:55:15 PM Signed: 6/28/2024 1:55:35 PM

Signature Adoption: Pre-selected Style Signature ID:

With Signing Reasons (on each tab):

10EC3CF5-F664-481F-BAE0-AD933DC0A009

Using IP Address:

With Signing Authentication via DocuSign password

I approve this document

Electronic Record and Signature Disclosure:

Accepted: 11/2/2020 2:09:16 PM

ID: 102e05f3-7156-49ba-9ce4-508e079f28ec

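### The protocol assigns the PedsQL Cognitive Functioning Scale to the safety analyses of all dosed participants, but the SAP tabulates it only on the adherence-restricted efficacy set

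*SAP*

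**What the plan says.** **Protocol.** Section 8.2.7 states: "As part of the safety assessments, support persons will complete the PedsQL™ Cognitive Functioning Scale". The safety methods table (Table 13, Section 9.4.3) has a row that begins "C-SSRS, PedsQL™ Cognitive Functioning Scale, and cognitive" and continues with the other cognitive assessments and the sleepiness scales. The same section says: "All safety analyses will be based on the safety analysis population". Section 9.3 defines that population as those randomised who "received at least one dose of the study treatment, whether prematurely withdrawn from the study or not". Table 6 also gives the scale an exploratory role: "Change from baseline to Week 12 in PedsQLTM Cognitive Functioning Scale".

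**SAP.** Section 4.1.4 describes the scale among the safety endpoints. The matching safety row in SAP Table 10 reads "C-SSRS, Neurocognitive Battery, KSS, ESS or ESS-CHAD, and Sudden Onset of Sleep Questionnaire", so the scale is gone from it. Table 7 lists it among the efficacy endpoints, and Section 4.3 names PedsQL among the supportive exploratory efficacy endpoints. In Appendix 1 its one output, t_pql_cfs_cfb (PedsQL "Cognitive Functioning Score Change from Baseline"), is assigned to Efficacy, while the Neurocognitive Battery table (t_neuro_cfb) is assigned to Safety.

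**Restriction on efficacy analyses.** SAP Section 3 states that "assessments at week 12 will be excluded from the efficacy analyses if the participant missed more than 7 consecutive study medications" immediately before the assessment, or if administered doses were below 60% of planned doses. No exception is made for PedsQL.

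**The concern.** A safety summary is normally kept free of adherence filters, because interrupting the drug can itself be a consequence of harm. Protocol Section 7.1.1 accepts temporary interruption as a way to manage adverse events. Section 4.1.2 gives severe sedation or somnolence and cognitive impairment as examples of findings that may, at the joint discretion of the sponsor and investigator, lead to dosing being stopped. A participant whose dosing lapsed for such a reason can still complete the Week 12 form. Under the SAP that form is left out of the only table for this scale, while the same participant stays in the Neurocognitive Battery table. The SAP gives no reason for treating the two cognitive measures differently. What is at stake is a protocol-specified safety summary that is no longer planned on its stated population.

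**Working it through.** The plan gives no figure on this point to reproduce, so the check is mainly a comparison of the texts.

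**1. Where each document places the scale**

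| Source | Role given | Population |
|---|---|---|
| Protocol 8.2.7 | Safety | not stated there |
| Protocol 9.4.3, Table 13 | Safety | Safety |
| Protocol Table 6 | Exploratory endpoint | not stated there |
| SAP 4.1.4 | Safety endpoint | not stated there |
| SAP Table 10 | Absent | not applicable |
| SAP Table 7 and Section 4.3 | Efficacy (supportive, exploratory) | not stated there |
| SAP Appendix 1, t_pql_cfs_cfb | Output | Efficacy |
| SAP Appendix 1, t_neuro_cfb (comparator) | Output | Safety |

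**2. Does the population label change the data?** Membership of the two populations is almost the same: randomised with at least one dose. The protocol's efficacy population has no compliance rule. The SAP adds one that acts on Week 12 assessments, and this makes the label matter. SAP Table 4 gives PedsQL one post-baseline window, study day 71 or later. Excluding a Week 12 form therefore removes the participant's only change from baseline.

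**3. Who is affected?**
- Form in the window and adherent: kept under either population.
- No form in the window: missing under either population. This covers most people who stop permanently and early.
- Form in the window, but off drug or poorly compliant for any reason: kept on Safety, dropped on Efficacy. Only this group is at issue.

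**4. The rule in doses.** The regimen is redacted, so assume one planned dose a day for 84 days. The 60% limb is 0.60 × 84 = 50.4, so it applies at 50 or fewer doses taken, that is 84 − 50 = 34 or more missed. The other limb starts at 8 missed doses, or 8 × 24 = 192 hours. Protocol Section 8.3.7.1 puts the half-life below about 20 hours, and 192 / 20 = 9.6 half-lives. Such a participant is off drug at the assessment. The scale recalls one month (Section 8.1.5.9), so at 8 missed days in an assumed 30-day month, 30 − 8 = 22 days of the recall period were still on drug.

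**5. Size, as a range.** Let m be the mean change of the forms kept, f the fraction of an arm's completed forms that are excluded, and d the amount by which the excluded group's mean change is worse than m (0 to 100 scale, higher is better). The mean of all forms is (1 − f)m + f(m − d) = m − fd, so the restricted mean exceeds it by fd:

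| f | d = −10 | d = 0 | d = 10 | d = 20 |
|---|---|---|---|---|
| 5% | −0.5 | 0 | 0.5 | 1.0 |
| 10% | −1.0 | 0 | 1.0 | 2.0 |
| 20% | −2.0 | 0 | 2.0 | 4.0 |

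The rule also applies to placebo, so the active-minus-placebo contrast shifts by f_A·d_A − f_P·d_P. With f = 10% and d = 10 in both arms this is 1.0 − 1.0 = 0. With the same active values and d_P = 0 it is 1.0 − 0 = 1.0. Every f and d here is an assumption. The 20% in protocol Section 9.2 is a planning figure for participants without evaluable data, which includes people with no form at all, so it does not estimate f.

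**The case against.** **The scale is also exploratory.** Protocol Table 6 lists it there and not among the secondary safety endpoints, and SAP Table 7, Section 4.3 and Appendix 1 follow that role. This stands as far as it goes. It justifies an efficacy-set table alongside the safety one, but does not cancel the explicit entry in protocol Table 13.

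**Protocol Appendix 3, Section 11 says that patient-reported outcomes will not be used for safety analyses.** The scale is self-reported by high-functioning participants, so the protocol is in tension with itself. This cannot account for the SAP's choice, however. High-functioning adults also self-report the KSS and ESS, and the SAP keeps both in Table 10 and on the Safety population. For low-functioning participants the support person completes the PedsQL form.

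**The SAP's internal contradiction is weak.** SAP Section 4.1.4 also contains the PedsQL Generic Core Scale, a quality-of-life measure, so the two may have been placed together for editorial reasons. That is fair. The point therefore rests on protocol Section 8.2.7 and Table 13 rather than on SAP Section 4.1.4.

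**Cognitive safety is covered elsewhere.** The performance-based Neurocognitive Battery, the KSS, the ESS, the Sudden Onset of Sleep Questionnaire and adverse events all remain on the Safety population. This stands and is the main reason for a low rating.

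**Conclusion.** The mismatch is established from the text. Followed as written, the SAP filters a protocol-specified safety summary by adherence and plans no version on the Safety population.

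A reader might go further and infer that the SAP removes those who could not tolerate the drug, and so biases the table towards no cognitive effect. The documents do not support that. The rule catches missed doses for any reason. People with no form at day 71 or later are absent under either population, so changing the label would not recover them. Someone off drug for more than a week may have recovered, wholly or partly, while the one-month recall may still include on-drug time. The sign of d is therefore open. Placebo records are filtered by the same rule.

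The filter may hide a cognitive effect, but the direction and size of any bias cannot be determined. The 0.5 to 4.0 points in the table for positive d illustrate what the assumptions would imply and are not estimates. Severity is minor: the table is descriptive, no inferential result depends on it, and other cognitive and sleepiness measures stay on the Safety population.

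**What to change.** Add the PedsQL Cognitive Functioning Scale to the safety row of SAP Table 10, in line with protocol Table 13. In Appendix 1, assign t_pql_cfs_cfb to the Safety population and state that the Week 12 compliance restriction in SAP Section 3 does not apply to it. If the exploratory role is to be kept, retain the efficacy-set version as an additional output labelled as such. The cost is two SAP entries and one population flag; no new data are needed.
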